6.6. Subject Withdrawal

Subjects may withdraw from the study at any time at the request of their parent(s)/legal guardian, or they may be withdrawn at any time at the discretion of the investigator or sponsor for safety (see also the Withdrawal From the Study Due to Adverse Events section) or behavioral reasons, or the inability of the subject to comply with the protocol-required schedule of study visits or procedures at a given study site.

If a subject does not return for a scheduled visit, every effort should be made to contact the subject's caregiver. All attempts to contact the subject and information received during contact attempts must be documented in the subject's medical record. In any circumstance, every effort should be made to document subject outcome, if possible. The investigator should inquire about the reason for withdrawal, request that the subject return for a final visit, if applicable, and follow up with the subject regarding any unresolved AEs.

If the subject withdraws from the study, and their parent(s)/legal guardian also withdraws consent for disclosure of future information, no further evaluations should be performed, and no additional data should be collected. The sponsor may retain and continue to use any data collected before such withdrawal of consent.

The decision to withdraw a subject from the study should be discussed with the sponsor's medical monitor.

When a decision has been made to discontinue further vaccination with the investigational product, the subject should, if possible, be followed for 6 months after the subject's final study vaccination before being permanently withdrawn from the study. In this period, every effort should be made to collect safety data and all data specified by the protocol including post-vaccination blood collection.

Eligibility criteria should be taken into consideration when determining if a subject should be withdrawn.

The following is a list of some examples, but not all, of the AEs that may warrant the withdrawal of a subject from the study unless there was an obvious alternative cause:

- Persistent, inconsolable screaming or crying for 3 or more hours within 48 hours after vaccination.
- Collapse or shock-like state (hypotonic-hyporesponsive episode) within 48 hours after vaccination.
- Temperature greater than or equal to 40.0°C (104.0°F) unexplained by another cause, within 48 hours after vaccination.
- Anaphylactic/anaphylactoid reaction, including shock.
- Encephalopathy.

• A seizure, with or without fever, within 3 days after vaccination.

7. ASSESSMENTS

Every effort should be made to ensure that the protocol-required tests and procedures are completed as described. However, it is anticipated that from time to time there may be circumstances outside of the control of the investigator that may make it unfeasible to perform the test. In these cases the investigator will take all steps necessary to ensure the safety and well-being of the subject. When a protocol-required test cannot be performed, the investigator will document the reason for this and any corrective and preventive actions that he or she has taken to ensure that normal processes are adhered to as soon as possible. The study team will be informed of these incidents in a timely manner.

For samples being collected and shipped, detailed collection, processing, storage, and shipment instructions and contact information will be provided to the investigator site prior to initiation of the study.

A complete medical history and physical examination will be performed on all subjects before randomization. The CRFs will capture the medical history and physical examination done at visit 1 to establish a baseline.

Safety parameters will be assessed as described in the Schedule of Activities Procedures section, Adverse Events section. In addition use of antipyretic medication, local reaction and systemic event data will be collected in an electronic diary for 7 days after each dose of investigational product in Cohorts 2, 3 and 4.

7.1. Electronic Diary – Cohorts 2, 3, and 4

The caregiver will be issued an e-diary, and will be asked to monitor and record the subject's local reactions and systemic events (including the use of antipyretic medication), for 7 days after each investigational product (13vPnC or Hib vaccine) vaccination. The e-diary allows recording of these assessments only within a fixed time window, thus providing the accurate representation of the subject's experience at that time. Use of antipyretic medication, local reactions and systemic events reported on the e-diary will be transferred electronically to the e-diary vendor (a trusted third party), where they will be available for review by investigators at all times via an Internet-based portal. At intervals agreed upon between the vendor and Pfizer, these data will be transferred electronically into Pfizer's database for analysis and reporting. These data do not need to be reported by the investigator on the CRF.

Investigators will be required to review the e-diary data online at frequent intervals to evaluate the subject's caregiver e-diary completion compliance and as part of the ongoing safety review.

7.2. Local Reactions

Cohorts 2, 3 and 4: Local reactions (redness, swelling, and tenderness) at the site of the investigational product (13vPnC or Hib vaccine) injection will be monitored daily for 7 days (day 1 to day 7) after each vaccination. An end date will be captured for all reactions either via the e-diary or CRF as applicable.

7.2.1. Redness and Swelling

Redness and swelling will be measured and recorded in measuring device units (range: 1 to 14), and then categorized as absent, mild, moderate, or severe based on the scale given below. Each unit represents 0.5 centimeters. A measuring device will be given to the caregiver with instructions for measuring any redness or swelling at the injection site. The caregiver will be asked to measure and to report the largest diameter of a local reaction. In case a measurement is between 2 values, the higher value should be reported. The caregiver will then record the measurements in the e-diary.

Table 6. Redness and Swelling

Absent	No redness or swelling present (0 units)
Mild	0.5 to 2.0 cm (1 to 4 units)
Moderate	2.5 to 7.0 cm (5 to 14 units)
Severe	>7.0 cm (>14 units)

If a reaction is greater than 14 units (7.0 cm), an additional visit to the study site will be required for an assessment by the investigator or other medically qualified study staff (refer to Unscheduled Visits – Cohorts 2, 3 and 4). If the caregiver is contacted by the site to schedule this visit and the local reaction is no longer present or the caregiver is unable to schedule the visit, this information will be recorded in the CRF.

7.2.2. Tenderness

The caregiver will be asked to assess whether tenderness is present at the investigational product (13vPnC or Hib vaccine) injection site and grade it according to the following scale. The caregiver will then record the assessment in the e-diary. For events that were ongoing on the last day that they diary was completed, the end date will be collected in the CRF.

Table 7. Tenderness

Absent	No discernible tenderness
Present	Tenderness present
Significant 7	Tenderness interfering with limb movement

7.3. Systemic Events

7.3.1. Temperature: Cohorts 2, 3 and 4

A digital thermometer will be given to the caregiver with instructions on how to measure the subject's axillary temperature at home. Temperature will be collected at bedtime daily for 7 days (day 1 to day 7) and at any time during the 7 days that fever is suspected. The highest temperature for each day will be recorded in the e-diary. Temperature will be measured and recorded to 1 decimal place and then categorized according to the following scale:

Table 8.Temperature

Absent	<38.0°C (100.4°F)
Mild	\geq 38.0°C (100.4°F) to \leq 39.0°C (102.2°F)
Moderate	>39.0°C (102.2°F) to \leq 40.0°C (104.0°F)
Severe	>40.0°C (104.0°F)

In addition to categorizing temperatures according to the scale in Table 8 additional analysis will be performed using the scale in Table 9.

Table 9. Temperature

37.1°C (98.8°F) to <37.6°C (<99.7°F) ≥37.6°C (≥99.7°F) to ≤39.0°C (≤102.2°F) >39.0°C (>102.2°F)

Fever is defined as temperature of greater than or equal to 38.0°C (100.4°F). In the event of a fever, temperature will be taken daily until fever has resolved (1 day of temperature less than 38.0°C [100.4°F]). An end date will be captured in the CRF for any fever persisting on the last day that they diary was completed.

7.3.2. Other Systemic Events: Cohorts 2, 3 and 4

The caregiver will be instructed to record the presence of other systemic events for 7 days (Day 1 to Day 7) after each investigational product vaccination and record the information in the diary. For events that resolve after the last day the diary was completed, the end date will be collected in the CRF.

Table 10.	Other Systemic Events for Infants Aged 7 months to <2 Years
	(Cohort 2 and 3)

Systemic Event	GRADE 1	GRADE 2	GRADE 3	GRADE 4 ^a	
	Mild	Moderate	Severe		
Decreased appetite (Loss of appetite)	Decreased interest in eating	Decreased oral intake	Refusal to feed	Emergency room visit or hospitalization for severe loss of appetite	
Drowsiness (increased sleep)	Increased or prolonged sleeping bouts	Slightly subdued interfering with daily activity	Disabling not interested in usual daily activity.	Emergency room visit or hospitalization for severe increased sleep	
Irritability (fussiness) (synonymous with restless sleep; decreased sleep)	Easily consolable	Requiring increased attention	Inconsolable; crying cannot be comforted	Emergency room visit or hospitalization for severe irritability	

a. Grade 4 assessment should be made by an investigator; Grade 4 will not be collected in the diary but as an adverse event on the case report form.

Systemic Event	GRADE 1	GRADE 2	GRADE 3	GRADE 4 ^a	
	Mild	Moderate	Severe		
Fatigue (= tiredness in diaries)	Does not interfere with activity	Some interference with activity	Prevents daily routine activity	Emergency room visit or hospitalization for severe fatigue	
Headache	Does not interfere with activity	Some interference with activity	Prevents daily routine activity	Emergency room visit or hospitalization for severe headache	
Vomiting	1 to 2 times in 24 hours	>2 times in 24 hours	Requires intravenous hydration	Emergency room visit or hospitalization for severe vomiting	
Diarrhea	2 to 3 loose stools in 24 hours	4 to 5 loose stools in 24 hours	6 or more loose stools in 24 hours	Emergency room visit or hospitalization for severe diarrhea	

Table 11. Other Systemic Events for Children Aged ≥2 to <6 Years (Cohort 4)

Systemic Event	GRADE 1 Mild	GRADE 2 Moderate	GRADE 3 Severe	GRADE 4 ^a
Muscle pain	Does not interfere with activity	Some interference with activity	Prevents daily routine activity	Emergency room visit or hospitalization for severe muscle pain
Joint pain	Does not interfere with activity	Some interference with activity	Prevents daily routine activity	Emergency room visit or hospitalization for severe joint pain

Table 11	Other Systemic Events fo	r Children Aged >2 to <6 Ve	ars (Cohort 4)
1 auto 11.	Other Systemic Events in	I Chhui ch Ageu 22 to 50 I C	$ais(Convit \tau)$

a. Grade 4 assessment should be made by an investigator; Grade 4 will not be collected in the diary but as an adverse event on the case report form.

7.3.3. Use of Antipyretic Medication

The caregiver will be instructed to record the use of antipyretic medications for prevention or treatment of symptoms daily during the active safety observation periods (Day 1 to Day 7) after each vaccination and record the information in the e-diary. An end date will be collected in the CRF for any antipyretic medication use persisting on the last day that they diary was completed. Data on the use of other concomitant medication will not be collected.

7.4. Biological Samples

Serum samples will be used only for scientific research. Each sample will be labeled with a code so that the laboratory personnel testing the samples will not know the subject's identity. All serologic testing will be conducted by the National Institutes for Food and Drug Control (NIFDC). After completion of the study, all remaining serum samples will be under the custody of NIFDC.

The subject's parent/legal guardian may request that his or her child's samples, if still identifiable, be destroyed at any time; however, any data already collected from those samples will still be used for this research.

- Subjects in Cohort 1 will have 8 blood draws of up to 5 mL each (Visit 1, Visit 4, Visit 5, Visit 6, Visit 8, Visit 9, Visit 10, Visit 11) over the approximately 5 year duration of the study.
- Subjects in Cohorts 2, 3 and 4 will have 2 blood draws of up to 5 mL each:
 - Cohort 2 will have 2 blood draws (Visit 1, Visit 4);
 - Cohort 3 will have 2 blood draws (Visit 1, Visit 3);
 - Cohort 4 will have 2 blood draws (Visit 1, Visit 2).

7.5. Immunogenicity Evaluation

Immunologic assays will be performed at NIFDC.

7.5.1. IgG Assessments

Serum concentrations of anticapsular IgG for each of the 13 pneumococcal serotypes (1, 3, 4, 5, 6A, 6B, 7F, 9V, 14, 18C, 19A, 19F, and 23F) will be determined in all subjects for each blood sample collected and expressed as micrograms per milliliter (μ g/mL). The assay will employ 2 adsorbents: a C polysaccharide-containing cell wall extract plus serotype 22F capsular polysaccharide.

Cohort 1: Serotype-specific IgG concentrations to the 13 pneumococcal serotypes (1, 3, 4, 5, 6A, 6B, 7F, 9V, 14, 18C, 19A, 19F, and 23F) will be determined in all subjects from the blood samples taken before vaccination, 1 month after the infant series, before the toddler dose, 1 month after the toddler dose and at yearly intervals for 4 years after the last vaccination.

Cohorts 2, 3, 4: Serotype-specific IgG concentrations to the 13 pneumococcal serotypes (1, 3, 4, 5, 6A, 6B, 7F, 9V, 14, 18C, 19A, 19F, and 23F) will be determined in all subjects from the blood samples taken before vaccination and after vaccination in each of the 3 cohorts (See schedule of activities for timing of blood samples.)

Additional 280 subjects (177 subjects of Cohort 2, 73 subjects of Cohort 3, and 30 subjects of Cohort 4): Serum concentrations of anticapsular IgG for each of the 13 pneumococcal serotypes (1, 3, 4, 5, 6A, 6B, 7F, 9V, 14, 18C, 19A, 19F, and 23F) will be determined in all subjects from the blood samples taken before vaccination and after vaccination in the additional subjects.

7.5.2. OPA Assessments

Serum levels of OPA for each of the 13 pneumococcal serotypes (1, 3, 4, 5, 6A, 6B, 7F, 9V, 14, 18C, 19A, 19F, and 23F) will be determined in all selected subjects for each blood sample collected and expressed as titers.

Cohort 1: Serotype-specific OPA titers to the 13 pneumococcal serotypes (1, 3, 4, 5, 6A, 6B, 7F, 9V, 14, 18C, 19A, 19F, and 23F) will be determined in a randomly selected subset of approximately 50 subjects from the blood samples taken before vaccination, 1 month after the infant series, before the toddler dose, 1 month after the toddler dose and at yearly intervals for 4 years after the last vaccination.

Cohorts 2, 3, 4: Serotype-specific OPA titers to the 13 pneumococcal serotypes (1, 3, 4, 5, 6A, 6B, 7F, 9V, 14, 18C, 19A, 19F, and 23F) will be determined in a randomly selected subset of approximately 50 subjects receiving 13vPnC and approximately 25 subjects receiving Hib vaccine from the blood samples taken before vaccination and 1 month after the last vaccination in each of the 3 cohorts.

Additional 280 subjects (177 subjects of Cohort 2, 73 subjects of Cohort 3, and 30 subjects of Cohort 4): Serotype-specific OPA titers to the 13 pneumococcal serotypes (1, 3, 4, 5, 6A, 6B, 7F, 9V, 14, 18C, 19A, 19F, and 23F) will be determined in a randomly selected subset.

8. ADVERSE EVENT REPORTING

8.1. Requirements

The table below summarizes the requirements for recording safety events on the CRF and for reporting safety events on the Clinical Trial (CT) Serious Adverse Event (SAE) Report Form to Pfizer Safety. These requirements are delineated for 3 types of events: (1) SAEs; (2) non-serious adverse events (AEs); and (3) exposure to the investigational product under study during pregnancy or breastfeeding, and occupational exposure.

Safety Event	Recorded on the CRF	Reported on the CT SAE Report Form to Pfizer Safety Within 24 Hours of Awareness
SAE	All	All
Non-serious AE	All	None
Exposure to the	All (regardless of whether	Exposure during pregnancy,
investigational product	associated with an AE), except	exposure via breastfeeding,
under study during	occupational exposure	occupational exposure
pregnancy or breastfeeding,		(regardless of whether
and occupational exposure		associated with an AE)

All observed or volunteered events regardless of vaccine group or suspected causal relationship to the investigational product(s) will be reported as described in the following paragraphs.

Events listed in the table above that require reporting to Pfizer Safety on the CT SAE Report Form within 24 hours of awareness of the event by the investigator **are to be reported regardless of whether the event is determined by the investigator to be related to an investigational product under study**. In particular, if the SAE is fatal or life-threatening, notification to Pfizer Safety must be made immediately, irrespective of the extent of available event information. This time frame also applies to additional new (follow-up) information on previously forwarded reports. In the rare situation that the investigator does not become immediately aware of the occurrence of an event, the investigator must report the event within 24 hours after learning of it and document the time of his/her first awareness of the event.

For each event, the investigator must pursue and obtain adequate information both to determine the outcome and to assess whether it meets the criteria for classification as an SAE (see the Serious Adverse Events section below). In addition, the investigator may be requested by Pfizer Safety to obtain specific follow-up information in an expedited fashion.

This information is more detailed than that recorded on the CRF. In general, this will include a description of the event in sufficient detail to allow for a complete medical assessment of the case and independent determination of possible causality. Any information relevant to the event, such as concomitant medications and illnesses, must be provided. In the case of a subject death, a summary of available autopsy findings must be submitted as soon as possible to Pfizer Safety. Any pertinent additional information must be reported on the CT SAE Report Form; additional source documents (eg, medical records, CRF, laboratory data) are to be sent to Pfizer Safety **ONLY** upon request.

As part of ongoing safety reviews conducted by the sponsor, any non-serious AE that is determined by the sponsor to be serious will be reported by the sponsor as an SAE. To assist in the determination of case seriousness, further information may be requested from the investigator to provide clarity and understanding of the event in the context of the clinical study.

8.1.1. Additional Details on Recording Adverse Events on the CRF

All events detailed in the table above will be recorded on the AE page(s) of the CRF. It should be noted that the CT SAE Report Form for reporting of SAE information is not the same as the AE page of the CRF. When the same data are collected, the forms must be completed in a consistent manner. AEs should be recorded using concise medical terminology and the same AE term should be used on both the CRF and the CT SAE Report Form for reporting of SAE information.

8.1.2. Eliciting Adverse Event Information

The investigator is to record on the CRF all directly observed AEs and all AEs spontaneously reported by the study subject/parent(s)/legal guardian. In addition, each study subject/parent(s)/legal guardian will be questioned about the occurrence of AEs in a non-leading manner.

8.1.3. Withdrawal From the Study Due to Adverse Events (see also the Subject Withdrawal Section)

Withdrawal due to AEs should be distinguished from withdrawal due to other causes, according to the definition of AE noted below, and recorded on the CRF.

When a subject withdraws from the study because of an SAE, the SAE must be recorded on the CRF and reported, as appropriate, on the CT SAE Report Form, in accordance with the Requirements section above.

8.1.4. Time Period for Collecting AE/SAE Information

The time period for actively eliciting and collecting AEs and SAEs ("active collection period") for subjects in Cohort 1, begins from the time the subject's /parent(s)/legal guardian provides informed consent, which is obtained before the subject's participation in the study (ie, before undergoing any study-related procedure and/or receiving investigational product), through and including Visit 4 and from Visit 5 to Visit 6. Between Visits 4 and 5 and between Visits 6 and 7, only SAEs and newly diagnosed chronic medical conditions will be

recorded. The subject's parent/legal guardian will be asked to report any AEs that occur within 48 hours after the blood draw at Visits 8, 9, 10, and 11.

The time period for actively eliciting and collecting AEs and SAEs ("active collection period") for subjects in Cohort 2, 3, and 4, begins from the time the subject's /parent(s)/legal guardian provides informed consent, which is obtained before the subject's participation in the study (ie, before undergoing any study-related procedure and/or receiving investigational product) until 1 month after the last vaccination (13vPnC or Hib). At the 6-Month follow-up telephone contact (final telephone contact), the parent(s)/legal guardian will be contacted to inquire about SAEs, including hospitalizations and newly diagnosed chronic medical conditions since the previous visit.

For subjects who are screen failures, the active collection period ends when screen failure status is determined.

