4.3. Criteria for Temporarily Delaying Vaccine Administration

The following conditions are temporary or self-limiting and a subject may be randomized and/or vaccinated once the condition(s) has resolved:

- 1. Current febrile illness (axillary temperature greater than or equal to 37.1°C [98.8°F]) or other acute illness within 48 hours before investigational product administration. Investigational product administration need not be delayed in the event of an afebrile illness if, according to local vaccination practice and the investigator's judgment, the subject should be vaccinated.
- 2. Subject has received any vaccine within the previous 4 days, except for bacille Calmette Guérin (BCG) vaccine and oral vaccines, which are allowed at any time.
- 3. Subject has received systemic antibiotic therapy within the last 5 days.

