- Record any nonstudy vaccinations. Note: vaccinations may be given ≥4 days before or ≥ 7 days after study vaccination, except for BCG vaccine and oral vaccines, which are allowed at any time, according to local practice or national recommendations, at the discretion of the investigator.
- Perform a physical examination evaluating any clinically significant abnormalities in the following: general appearance, skin, head, eyes, ears, nose, throat, heart, lungs, abdomen, extremities, back/spine, neurological status, and lymph nodes including worsening of

medical history conditions. Results must be recorded on source documents and the Medical History or AE page of the CRF as appropriate.

- Based on clinical evaluation, determine whether any AEs (including serious adverse events [SAEs]) have occurred since the parent/legal guardian provided informed consent and record them on the CRF.
- Measure and record the subject's axillary temperature.
- Ensure that all inclusion criteria and none of the exclusion or temporary delay criteria are met.
- After all entry criteria are confirmed, the subject is randomized using the IRT or equivalent system.
- Collect a blood sample (approximately 5 mL). Blood must be drawn from peripheral veins (eg, arm, foot, or scalp veins). Drawing blood from central veins (eg, jugular or femoral veins), which may increase the risk associated with study participation, is not permitted.
- Administer a single intramuscular dose of investigational product (13vPnC or Hib) into the subject's left limb (left anterolateral thigh muscle or deltoid of the left arm) in accordance with the local package insert.
- Observe the subject for at least 30 minutes after vaccination for any significant acute reactions. Any AE noted during the observation period should be recorded in the source documents and in the AE section of the CRF.
- Issue a measuring device and a digital thermometer to the caregiver and provide instructions on their use.
- Issue a subject e-diary to the caregiver and provide instruction on its completion.
- Ask the caregiver to contact the investigator or other site staff immediately if any significant illness or hospitalization occurs during the study period, or if the subject reports redness or swelling at the investigational product injection site measuring >14 units on the measuring device.
- Remind the caregiver to bring the e-diary to the next study visit.

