8.2. Definitions

8.2.1. Adverse Events

An AE is any untoward medical occurrence in a study subject administered a product or medical device; the event need not necessarily have a causal relationship with the treatment or usage. Examples of AEs include, but are not limited to:

- Abnormal test findings;
- Clinically significant signs and symptoms;
- Changes in physical examination findings;
- Hypersensitivity;
- Progression/worsening of underlying disease;
- Drug abuse;
- Drug dependency.

Additionally, AEs may include signs and symptoms resulting from:

- Drug overdose;
- Drug withdrawal;
- Drug misuse;
- Drug interactions;
- Extravasation;
- Exposure during pregnancy (EDP);

- Exposure via breastfeeding;
- Medication error;
- Occupational exposure.

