3.1.2. Primary Safety Endpoints

- The incidence of local reactions and systemic events (including the use of antipyretic medication) in the 7 days after each vaccination (13vPnC or Hib) in Cohorts 2, 3 and 4.
- The incidence of AEs from the signing of the informed consent document (ICD) to 1 month after the last vaccination (13vPnC or Hib) in Cohort 2, 3 and 4.
- The incidence of newly diagnosed chronic medical conditions from 1 month after the last study vaccination (13vPnC or Hib) to 6 months after the last study vaccination in Cohort 2, 3 and 4.

PFIZER CONFIDENTIAL Page 8

[figure not shown]
• The incidence of serious adverse events (SAEs) from the signing of the ICD to 6 months after the last study vaccination (13vPnC or Hib) in Cohort 2, 3 and 4.

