6.4. Safety Summaries and Analyses

All safety analyses will be summarized based on the safety population in accordance with Pfizer reporting standards. All safety summaries will be provided by vaccine group separately for each dose in infant series and toddler dose.

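### AE and SAE incidence is counted from consent rather than first vaccination, so an event before dose 1 is reported under the vaccine later received; the expected effect is small

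*Protocol*

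**What the plan says.** Protocol 8.1.4 opens active collection for "subjects in Cohort 2, 3, and 4, begins from the time the subject's /parent(s)/legal guardian provides informed consent" and makes clear that consent comes before any study procedure or product. SAP 3.1.2 starts the primary AE endpoint for Cohorts 2 to 4 at the same point: "The incidence of AEs from the signing of the informed consent document (ICD) to 1 month after the last vaccination". The primary SAE endpoint also starts at consent and runs to 6 months after the last vaccination. SAP 6.1.2.1 repeats both windows for the analysis. SAP 3.2.2 and 6.2.2 use the same start for Cohort 1's AEs up to 1 month after dose 3 and for its SAEs.

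In Cohorts 2 to 4, the Visit 1 steps (Protocol 6.2.1, 6.3.1, 6.4.1) run in this order: consent, a check for AEs that "have occurred since the parent/legal guardian provided informed consent and record them on the CRF", randomisation, blood draw, vaccination. Under Protocol 4.3, when a temporary delay condition applies, "a subject may be randomized and/or vaccinated once the condition(s) has resolved". No maximum delay is given.

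The safety population (SAP 4.5) is everyone who received at least one dose. The SAP presents number, proportion and 95% CI by vaccine group, and 13vPnC-minus-Hib risk differences for tier 1 and tier 2 events (SAP 6.4.1).

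**The concern.** Collecting from consent is ordinary practice. The difficulty is that the counting window starts there too. SAP 2.1.2 uses these incidences as the measure of the safety profile of 13vPnC, and an event that precedes the first injection carries no information about it. A pre-dose event in a child later dosed would raise the AE or SAE proportion of whichever vaccine the child received. A pre-dose SAE would be the most visible case: it would stand under a vaccine group in a report written to support licensure.

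**Working it through.** The plan gives no figure for pre-dose events, so there is nothing to reproduce. The check traces the rule and then sizes it.

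**Tracing the rule.** The endpoint starts at consent (SAP 3.1.2). So does the analysis window (SAP 6.1.2.1). Pre-dose events reach the CRF (Protocol 6.2.1, 6.3.1, 6.4.1). The safety population restricts which children count, not when an event began (SAP 4.5). Nothing visible removes the event at any step.

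**Inputs.**
- Post-dose follow-up of 28 days: the lower end of Cohort 4's 28-to-42-day window (Protocol Table 4). With one dose, Cohort 4 has a short post-dose window, so a gap weighs more there.
- Planned arm sizes 118 and 59 per cohort (Protocol Table 15).
- Mean consent-to-dose gap *g* in days, and background AE rate *r* per child-day: **both assumed**, since the documents give neither.

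**Added incidence** = [1 − exp(−r(28 + g))] − [1 − exp(−28r)], in percentage points:

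| g (days) | r = 0.005 | r = 0.01 | r = 0.02 |
|---|---|---|---|
| 0.1 | 0.04 | 0.08 | 0.11 |
| 1 | 0.43 | 0.75 | 1.13 |
| 5 | 2.15 | 3.69 | 5.44 |

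The incidence without a gap is 13.1%, 24.4% and 42.9% at the three rates. In 118 children, a 0.1-day gap adds about 0.05 to 0.13 of a child and a 1-day gap about 0.5 to 1.3 children.

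**What the gaps mean.** A mean of 0.1 day corresponds, for example, to 2% of children delayed by 5 days (0.02 × 5). A mean of 1 day needs 20% delayed by 5 days (0.20 × 5). The 5-day row would require that delay on average across the whole arm.

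**Share of the Cohort 4 window that is pre-dose** = g/(g + follow-up). For 1 day it is 1/43 = 2.3% to 1/29 = 3.4%. For Cohort 2 13vPnC at the minimum dose intervals (28 + 56 + 28 = 112 days, up to 126) it is 1/127 = 0.8% to 1/113 = 0.9%.

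**Risk difference.** If the pre-dose risk is q = 1 − exp(−rg) in both arms, each arm's reported incidence is 1 − (1 − p)(1 − q), so the difference is multiplied by (1 − q). A zero difference stays zero. Example with r = 0.01 and an assumed 1.3-fold post-dose rate under 13vPnC: exp(−0.28) − exp(−0.364) = 6.09 points with no gap, 6.03 with 1 day, 5.79 with 5 days.

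**One pre-dose SAE**: 1/118 = 0.8 points (13vPnC) or 1/59 = 1.7 points (Hib) in a cohort.

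**The case against.** Much of the case on the other side stands.

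- **The window is short.** Consent, randomisation, blood draw and dose 1 all belong to Visit 1, and Protocol 6 ties the physical examination to the day of first vaccination. For most children the gap is part of a day.
- **Delay does not by itself produce a counted event.** A reader might infer that every child delayed for illness contributes a pre-dose AE. An illness already present at consent began before the window and is medical history. Two of the three delay conditions (a recent vaccine, recent antibiotics) are not illnesses. Only a new or worsening event after consent counts.
- **A pre-dose share of 1% to 5% is tempting but has no source.** At the rates above, 5% needs a mean gap of −ln(0.95)/r, about 2.5 to 10 days across all children. The single-visit layout does not support that.
- **The documents do not contradict themselves here.** A reader might set the window against Protocol 8.2.1, "An AE is any untoward medical occurrence in a study subject administered a product or medical device", or SAP 6.4, "All safety summaries will be provided by vaccine group separately for each dose in infant series and toddler dose". The first sets no onset rule, and everyone analysed was dosed. By-dose tables can stand beside a cumulative endpoint, although the SAP does not say where a pre-dose event would go in them.
- **A rule may exist out of sight.** SAP 3.4.1 is partly blacked out, and Protocol 9.3 and SAP 6.4 defer to the sponsor's reporting standards. The supportable statement is that no *visible* rule exists.
- **Cohort 1 is weaker ground.** Its Visit 1 steps (Protocol 6.1.1) list no AE check before the dose, and all its children are assigned 13vPnC. Only its consent-start windows are at issue.

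None of this changes the windows in SAP 3.1.2 and 6.1.2.1, which say in terms that counting starts at consent.

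**Conclusion.** The point holds in a limited form. Followed as written, the plan reports events that precede exposure as incidence under a vaccine group. The likely inflation is about 0.04 to 0.11 percentage points for a mean gap of 0.1 day and about 0.4 to 1.1 points for 1 day. Both figures rest on assumed gaps and assumed rates of 0.005 to 0.02 per child-day.

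The practical weight falls on children delayed under Protocol 4.3 who have a new event after consent, and on a rare pre-dose SAE. Such an SAE is unlikely, because the child must still meet the entry criteria and be dosed to enter the safety population.

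A reader might infer that the 13vPnC-versus-Hib comparison is biased. In Cohorts 2 to 4 randomisation makes pre-dose events equally likely in both arms, so they leave no expected bias, only slight dilution of a real difference. The 7-day reactogenicity endpoints and the chronic-condition endpoints are unaffected, as their windows start later.

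**What to change.** Keep collection from consent. In SAP 6.1.2.1, 6.2.2 and 6.4.1, tabulate AEs and SAEs, including the tier 1 and tier 2 risk differences, with onset at or after the first study vaccination. Count same-day events of unknown time as post-dose. List events between consent and dose 1 separately by cohort. If a post-dose onset rule already exists in the sponsor's standards or in the blacked-out text, state it in these sections.

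SAP 2 says the analyses for the primary report are done and will be repeated with the additional 280 subjects. Apply the change in that supplemental report and in the final report, with the consent-start table alongside so that results remain comparable with the primary report.

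The cost is SAP wording, one onset-date filter and one listing, with no new data, plus two AE tables to reconcile. A limit remains: under the same-day convention, an event after the Visit 1 blood draw but before the injection stays in the post-dose count unless its onset time is recorded.
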